The evaluation of in utero MR needs also to include patient views about the acceptability of MR imaging for informing their understanding of fetal anomaly. New technologies in fetal medicine raise ethical and social dilemmas for the patients involved. The views of such women and their partners are important when considering issues of clinical implementation [17]. Data from studies of MR experience outwith pregnancy suggest that this technology may be perceived positively in terms of e.g. comfort and impact on care [18]; however, it can also be associated with anxiety [19, 20] and may be evaluated as less acceptable than ultrasound [21]. Overall satisfaction with prenatal diagnosis is high [22]; key factors that impact on satisfaction include participation in decision making [23], staff attitudes [23, 24] and the amount of information provided [24]. The limited data available on the use of in utero MR imaging suggest that it may generate additional distress (especially where fetal prognosis is poor [25, 26]) and more anxiety than ultrasound [27].

The research undertaken in this study is therefore a logical extension of our previous work. It will come from a large, widely representative population group and should provide definitive data on diagnostic accuracy, diagnostic confidence, effect on management and acceptability of in utero MR in a timely fashion. The study is observational, however the results of in utero MR imaging will be available to fetal medicine clinicians during the study and may therefore influence clinical management decisions in individual cases (according to clinical judgement). This scenario is already considered acceptable clinical practice in previous and ongoing research studies both within our site and in other national and international centres. Any change in clinical management and decision making directly attributable to the information provided by in utero MR imaging will be recorded prospectively, and the accuracy of that information will be compared against a postnatal or post mortem reference diagnosis.

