Multi-centre prospective observational study of diagnosis, management and outcome in a large cohort of pregnancies affected by abnormal fetal brain development.

The study is designed to include all developmental brain abnormalities identified by ante-natal ultrasound screening from 18 weeks gestation onwards. Participants are recruited from at least 13 sites within the UK incorporating a wide geographic and socioeconomic base. MR scanning is then carried out either in a primary unit (Sheffield) or in one of five secondary units (Newcastle, Leeds, Birmingham, Belfast and Manchester). Figure 1 outlines the study design and length of time that each participant may remain in the study process.

Figure 1. MERIDIAN study design

Primary Outcomes

- 1) Absolute diagnostic accuracy of MR as assessed by percentage of cases where in utero MR diagnosis agrees with post-mortem autopsy/MR or postnatal imaging.
- 2) Absolute diagnostic accuracy of US as assessed by percentage of cases where US diagnosis at the time of referral for MR agrees with post-mortem autopsy/MR or postnatal imaging.

Agreement between prenatal diagnosis (both before and after MR) and outcome diagnosis will be judged by an appointed independent expert panel consisting of a fetal medicine clinician, paediatric neuroradiologist and paediatric neurologist or neurosurgeon.

Secondary Outcomes

Effect of including MR scan on diagnostic confidence

Change in diagnostic confidence will be measured before and after the MR scan as assessed by a 5 point Likert scale.

Effect of including MR scan on prognosis

Change in prognosis will be measured before and after the MR scan as assessed by a 4 point categorical scale (poor – less than 50% chance of normal neuro-developmental outcome, intermediate - 50-90% chance of normal outcome, favourable - greater than 90% chance of normal outcome, normal – no abnormality found after detailed fetal medicine investigation).

Effect of including MR scan on management

Change in management will be measured before and after the MR scan as assessed by a 2 point categorical scale. This scale will record whether termination of pregnancy was discussed on the basis of poor neuro-developmental prognosis.

4. Ancillary sub-studies

Sociological Study

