Table 2 below lists the adverse events and serious adverse events which have the potential to occur during this study. These events will be recorded and reported to the DMEC, and as appropriate to the TSC, and they are defined as “expected” events within this study protocol. Nevertheless, the TSC will ultimately judge whether the rate of occurrence of these events is within acceptable and anticipated levels. Any other medical event which occurs during the study which meet the criteria defined above for a SAE will be recorded and reported to the DMEC.

Table 2. Expected SAE’s & AE’s.

Serious adverse event (SAE)	Adverse event (AE)
1) MR diagnosis differs from outcome reference diagnosis; TOP performed	1) MR diagnosis differs from outcome reference diagnosis; US diagnosis same as outcome reference diagnosis
2) Spontaneous intrauterine fetal demise (IUFD) or Stillbirth	2) MR examination incomplete or sub-optimal as a result of patient anxiety and/or claustrophobia
3) Pre-term delivery (less than 37 weeks)	
4) Neonatal death	
5) Injury during MR examination related to pacemaker, medical implant or other metallic object (failure of MR safety screening procedures)	

Perhaps the most important clinical risk associated with this study is that the prospective management of a particular pregnancy is modified as a result of information made available by in utero MR imaging, and this information subsequently proves to be inaccurate. For instance, an abnormality is detected on ultrasound, but the fetal prognosis is not considered so poor as to justify termination of pregnancy; the prognosis based on in utero MR imaging is considered to be much worse, however, to an extent where termination of pregnancy is discussed and subsequently performed (and the following post mortem examination does not substantiate the MR findings). Any such case would only be identified after the reference diagnosis is achieved (for instance by autopsy), and only then during retrospective comparison of prenatal and outcome diagnosis. As soon as any such case is identified,

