The first consideration is a pre-cursor to the second, since the comparison in 2) is irrelevant if neither MR nor USS contain some measure of useful prognostic information. We will quantify 1) by assessing the concordance between severe neurodevelopmental impairment (BSID score of <80 on the Cognitive AND language index or a combined score of <85 or a motor score of <70) and poor prognosis, based on i) MR and ii) USS. The sensitivity, specificity, positive and negative predictive values of MR and of USS will be reported.

The second consideration is to compare the relative prognostic accuracy of USS and MR. We will do so by calculating the difference in the respective sensitivities and specificities using the paired sample methods recommended by Newcombe [18].

	Outcome	
	Severe impairment (BSID<70) N=xxx	No severe impairment (BSID>=70) N=xxx
USS prognosis		
Poor	n (%)	n (%)
Normal/favourable	n (%)	n (%)
% correctly classified*	$P_{sens (USS)}$	$P_{spec (USS)}$
MR prognosis		
Poor	n (%)	n (%)
Normal/favourable	n (%)	n (%)
% correctly classified*	$P_{sens (MR)}$	$P_{spec (MR)}$
Difference (95% CI)	$P_{sens (MR)} - P_{sens (USS)}$	$P_{spec (MR)} - P_{spec (USS)}$
P-value (McNemar)		

* Here, we consider "Correct" to mean 1) Poor prognosis corresponds to severe impairment, and 2) Normal/favourable prognoses correspond to no severe impairment. The percentages correctly classified reflect 1) sensitivity and 2) specificity respectively.

The secondary outcomes are

- 3) To assess qualitatively the cases for which the USS prognosis and MR prognosis differed, in relation specifically to the original diagnoses
- 4) To look at the concordance in the subgroup of children for which the MR scan was performed within 24 weeks
- 5) To assess ability to predict non-severe impairment

The last of these will further subdivide children without severe impairment (BSID>=70) into "mild-moderate impairment" (BSID between 70 and 85) and "Normal" (BSID>85). The corresponding prognostic categories are "Intermediate" and "Normal or Favourable", and the concordance between the three prognostic categories and the three outcomes will be reported by two-way tabulations.

Sample size Project 2

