Our sample size is constrained by the original MERIDIAN cohort, but our data collected to date provides some assurance that we will have adequate power to address the primary outcome defined by this project. As well as approaching all children known to have survived (expected number approximately 500), our analysis will include non-surviving infants (defined as having had poor outcomes; expected number approximately 50-100). Allowing for attrition in the surviving child group we approximate that there will be 400 cases, from data collected in the entire cohort, there are almost 200 instances where prognosis changed as a result of MR imaging, of whom 38 are now classified as the poorest prognosis. Scaling these prevalence's down, 400 cases will have a 90% power to detect a 20% increase in the sensitivity and a 10% increase in specificity using the tests outlined above at a two-sided significance level of 5%.

We will quantify the impact of selective participant retention by comparing prognoses and diagnoses of consenting participants with those who refused. Non-surviving fetuses or children will by definition have no BSID outcome data, but will be included in the primary analyses as having poor outcomes. Outcomes among fetuses for whom TOP was performed are controversial, but some diagnoses (for example TOP for anencephaly) are inevitably fatal. For these cases we will use our existing independent expert panels to adjudicate whether, and how, the data should be included.

Hypothesis

The clinical significance of fetal brain abnormalities are more accurately predicted by MR imaging when compared with USS. Specifically, we predict a 10% improvement in prognostic accuracy by using MR imaging.

Analysis of Project 3

Using the categories detailed in project 2 (severely impaired, mild-moderately impaired and normal) we will calculate the prevalence of severe and non-severe impairments from our data, together with exact binomial confidence intervals and compare this to the prognoses obtained from cases where USS identified isolated mild VM. Where prognosis changed as a result of MR imaging we will assess whether this was attributable to the MR identifying further diagnoses.

Sample size Project 3

With approximately 140 cases and assuming the prevalence of poor outcome is indeed less than 10%, we will be able to estimate the prevalence to within a standard error of 2.5%.

Hypothesis

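### Project 2 codes non-survivors as poor outcomes and leaves terminations to a panel with no stated rule or masking, so a termination prompted by MR can count as a correct MR prognosis

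*Protocol*

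**What the plan says.** Follow-up protocol, section 7, Analysis of Project 2: a prognosis is correct when "Poor prognosis corresponds to severe impairment", or when a normal or favourable prognosis goes with no severe impairment. The sensitivities and specificities of MR and US are then compared as paired proportions, with McNemar p-values.

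Follow-up protocol, section 7, Sample size Project 2: besides about 500 survivors, the analysis takes in non-surviving infants, "defined as having had poor outcomes; expected number approximately 50-100". The rule is then widened to fetuses: "Non-surviving fetuses or children will by definition have no BSID outcome data, but will be included in the primary analyses as having poor outcomes". Outcomes after termination are called controversial, with the remark that some diagnoses are fatal in any event, and the section continues: "For these cases we will use our existing independent expert panels to adjudicate whether, and how, the data should be included".

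Three places in the main protocol bear on this. Section 1: "the results of in utero MR imaging will be available to fetal medicine clinicians during the study and may therefore influence clinical management decisions". Section 3, on the management outcome: "This scale will record whether termination of pregnancy was discussed on the basis of poor neuro-developmental prognosis". Section 8, Study Safety, gives as an example of the study's main clinical risk an MR prognosis much worse than the US one, "to an extent where termination of pregnancy is discussed and subsequently performed", where the post mortem then fails to support MR.

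**The concern.** The index test can help to produce the outcome that it is scored against. When MR worsens the prognosis and the pregnancy is ended, no developmental outcome can ever be observed. If that case is entered as a poor outcome, MR is right and US is wrong by construction.

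The effect is not symmetrical between the tests. The decision follows the post-MR prognosis. Where MR improves a poor US prognosis, the pregnancy is more likely to continue and the child can be assessed. At stake is whether an MR advantage in Project 2's primary comparison could be told apart from MR's influence on which pregnancies continued.

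Spontaneous fetal, neonatal and child deaths raise a lesser issue. An MR report does not cause them. The concern there is only that the coding takes no account of cause of death, which the follow-up protocol collects for children (sections 4 and 6), so a death unrelated to the brain counts as a poor neurodevelopmental outcome.

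**Working it through.** **1. The two rules.** One sentence enters non-surviving fetuses as poor. A later one lets the panel decide "adjudicate whether, and how, the data should be included" for terminations. A terminated fetus falls under both, and no precedence, criterion or default is given.

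**2. Scoring one case.** Take a fetus with a favourable US prognosis and a poor MR prognosis that would not have been severely impaired.

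| | Column | MR | US |
|---|---|---|---|
| Born and assessed | not severe | wrong | right |
| Terminated, coded poor | severe | right | wrong |

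Coding adds a discordant pair for MR to sensitivity and removes one against MR from specificity. Both shifts favour MR.

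**3. The plan's power figure.** Stated: 400 cases, 90% power, +20 points sensitivity and +10 points specificity, two-sided 5%. The paired formula is n = (1.96√ψ + 1.2816√(ψ − d²))²/d², with ψ the discordant proportion and d the difference. The protocol gives no ψ by outcome column. From its almost 200 changed prognoses among 832 participants, assume ψ = 200/832 = 0.24.
- Sensitivity, d = 0.20: n = 59 severe cases.
- Specificity, d = 0.10: n = 248 non-severe cases.

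So 90% is attainable with 400 cases if 59 to 152 (400 − 248) are severe. The number severe is not stated, so the figure is plausible but cannot be uniquely reproduced.

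**4. Weight of coded deaths.** Let D be the non-survivors (50-100, stated) and p the severe proportion among survivors (10-20%, assumed). If D lies within the 400, the share of the severe column is D/(D + p(400 − D)).
- D = 50, p = 0.20: 50/120 = 42%.
- D = 50, p = 0.10: 50/85 = 59%.
- D = 100, p = 0.20: 100/160 = 63%.
- D = 100, p = 0.10: 100/130 = 77%.

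The text can also be read as 400 survivors with the deaths added. The range is then 50/130 = 38% to 100/140 = 71%.

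**5. Spurious sensitivity difference.** Assume a net MR-US gap of 10-30 points in poor prognoses among the coded deaths and none among survivors. Lowest: 0.42 × 10 = about 4 points. Highest: 0.77 × 30 = about 23 points.

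**6. Plausibility of the top.** A 30-point gap among 100 deaths needs 30 net MR-only poor prognoses. Only 38 fetuses in the whole cohort moved to the poorest prognosis. Scaled to 400 cases that is 38 × 400/832 = about 18, survivors included.

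**7. Equal tests.** Assume 18 discordant fetuses each way, 100 severe, 300 not severe, and 9 of the 18 MR-only poor fetuses not truly severe. If half of those 9 are terminated and coded poor (4.5 on average):
- sensitivity gap 4.5/104.5 = +4.3 points;
- specificity gap 4.5/295.5 = +1.5 points.

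In 20,000 simulated studies, McNemar's test then falsely favoured MR in 16% (sensitivity) and 21% (specificity), against a nominal 2.5% each. Keeping half terminated, and varying the severe count from 60 to 150 and the not-truly-severe count from 9 to 13 of 18, the gaps run from +2.9 to +9.8 points (sensitivity) and +1.3 to +2.7 points (specificity).

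**8. Power on measured outcomes.** Survivors alone would give 30 (10% of 300) to 70 (20% of 350) severe cases. At ψ = 0.24, power for +20 points sensitivity is 62%, 75% and 85% with 30, 40 and 50 severe cases, and 90% at 59. The stated power may therefore depend on the coded deaths.

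**The case against.** Four objections have weight.

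- **Masking.** A reader might infer that the panel works unmasked. The documents do not say so. The panel is called independent, and the main protocol's amendment list mentions a separate document on its requirements, which is not shown. What stands is that no masking is stated here. The same panel was set up to judge prenatal diagnoses before and after MR against outcome, so masking cannot be presumed.
- **Which deaths.** Terminations are set apart and the panel may exclude them, which is a partial safeguard. The 50-100 are described as infants and may not contain terminations: about 500 survivors plus 50-100 leaves 232-282 of the 832 participants unaccounted for. This limits how far steps 4 and 5 measure the self-fulfilling route. It does not supply the missing rule.
- **Existing checks.** Cases where US and MR prognoses differ are reviewed qualitatively, and the main study reports terminations with a discrepant MR diagnosis as serious adverse events. Neither changes how a case enters the primary table. The one stated selection check compares consenters with refusers.
- **Counting death as poor.** This is a common guard against bias from analysing survivors only, and a survivors-only analysis would have its own selection. That is a reason to keep such an analysis beside the primary one, not in its place.

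**Conclusion.** The point holds for Project 2's primary comparison. The termination rule is internally inconsistent and open-ended, and the protocol's own account of management gives a route by which MR earns credit from a termination that it prompted. The direction favours MR in both sensitivity and specificity.

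The size is not determinable from the documents. The 4-23 point range rests on an assumed 10-20% severe rate among survivors, an assumed 10-30 point gap among coded deaths, and the reading that the 400 include the non-survivors. The equal-tests illustration rests on assumed discordance and termination fractions.

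A reader might infer that the whole 20-point effect used for power could be an artefact. The top of the range allows it arithmetically, but it would need more MR-only poor prognoses than the 38 reported cohort-wide, about 18 when scaled, make likely. A reader might also extend the point to MERIDIAN's primary outcomes or to Project 1. Those compare prenatal diagnosis with a reference diagnosis and do not use this coding.

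**What to change.** In the follow-up protocol, section 7:

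1. Reconcile the sentence on non-surviving fetuses with the one on terminations, so that one rule covers each case.
2. Have the existing panel classify every termination and death as severe, not severe or indeterminate. It should see the post-mortem findings and the death record with its cause, but not the US or MR reports or either prognosis. Enter the first two classes as classified and exclude only the indeterminate. Excluding every case not judged severe would itself hide MR false positives.
3. Beside the primary result, report the MR-US difference in children with measured outcomes and with terminations excluded. Keep the coding of all non-survivors as poor as a sensitivity analysis.
4. Restate the power sentence for the resulting number of severe cases, giving that number, the assumed discordance, and whether the 400 include non-survivors.

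The cost is wording and a masked case sheet for a panel that already exists. The downside is fewer severe cases, hence wider intervals for sensitivity, and some indeterminate cases where there was no post mortem. The main protocol (section 9) cites 83% autopsy completion after termination for ventriculomegaly in one department, so that loss is real but limited if the figure carries over.

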There are 3 distinct projects within this follow-up study, the aims and objectives have been divided by project to clearly demonstrate how they will be implemented:

Project 1:

The aim of project 1 is to refine our estimates of diagnostic accuracy of MR imaging as a technology to aid the prenatal diagnosis of fetal developmental brain abnormalities.

- 1) We will reassess the diagnostic accuracy of MR imaging compared to antenatal US through:
 - a) Measurement of diagnostic accuracy of antenatal US alone (i.e. prior to iuMR) relative to updated reference diagnosis at 2-3 years of age (post-natal imaging or post-mortem examination);
 - b) Measurement of diagnostic accuracy of iuMR (following antenatal US) relative to the updated reference diagnosis at 2-3 years of age (post-natal imaging or post-mortem examination).

Project 2:

The aim of project 2 is to improve the prognostic information available during pregnancy based on the functional and developmental outcomes of the MERIDIAN cohort.

- 1) We will quantify the value of prognoses based on MR imaging and on USS by:
 - a) Assessing the concordance between severe neurodevelopmental impairment (defined by BSID score of <80 on the Cognitive AND language index or a combined score of <85 or a motor score of <70, evidence of severe disability based on a score <-2SDs for the ASQ, or evidence of cerebral palsy based on GMFCS) and poor prognosis, based on MR and on USS;
 - b) Comparing the relative prognostic accuracy of USS and MR imaging;
- 2) We will qualitatively assess the cases for which the USS prognosis and MR prognosis differed, in relation specifically to the original diagnoses;
- 3) We will look at the concordance in the subgroup of children for which the MR scan was performed within 24 weeks;
- 4) We will assess ability to predict non-severe impairment (defined as BSID <85 or a score between 1 and 2 SDs for the ASQ).

Project 3:

The aim of project 3 is to assess the clinical significance of isolated, mild ventriculomegaly.

- 1) We will assess the clinical significance through:
 - a) Identification of all isolated, mild ventriculomegaly cases diagnosed on in utero MR in the MERIDIAN cohort and define their developmental outcome at 2-3 years (as per project 2);
 - b) Comparison of developmental outcome to the prognoses made based on USS.

3. Study design

Multi-centre observational cohort study of diagnostic accuracy and functional development of children born from the MERIDIAN study.

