Where it is not possible to arrange a face to face appointment, or if for any reason the questionnaires are not completed during the appointment then there will be the option for the GMFCS questions (adapted for parent completion) and SDQ to be posted out or given to parents for them to complete and return to the research team. Alternatively the questionnaires can be completed over the telephone with the child's parent.

The research team will categorise the children as severely impaired (scoring <70), mild-moderately impaired (scoring 70-85) or normal (scoring 85+) based on the results of the developmental assessments. These categories will be used to complete the developmental assessment CRF.

After the developmental assessments all participants will be debriefed via a feedback letter from the research team, which will contain details of the results from the developmental assessment. Where an important previously unrecognised disability has been identified, we will speak to parents about future actions. Typically this would include informing the GP and advising about appropriate referrals either to community paediatrics or therapy services. A member of the study team (NE, an experienced paediatrician) would be available for discussion and advice if the best course of action was not immediately apparent.

Project 3

There is no input required from the MERIDIAN participants or research sites for completion of project 3. Project 3 will be completed by the central study team at the University of Sheffield.

[figure not shown]
The information for project 3 will come from the assessments described in project 2. We will identify all cases of isolated mild ventriculomegaly diagnosed on iuMR and define their developmental outcome at 2-3 years as severely impaired, mild-moderately impaired or normal as per project 2. In MERIDIAN, the most common information given to women on the basis of isolated mild VM on USS is "favourable (90%)" followed by poor or intermediate and the remainder as normal.

We will calculate the prevalence of severe and non-severe impairments in isolated mild VM cases.

Please see Figure 2. for details of procedures and data collection document

Figure 2. Procedure for MERIDIAN 2-3 year follow up study

Screening

Project 1 – Case note review

Project 1 and 2 – Case note review and BSID

Project 1
If consented to project 1 only research midwife will conduct medical case note review and record details of any further follow up

Project 1 and 2

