Isolated, mild fetal ventriculomegaly confirmed by MR is not associated with an increased risk of 'poor' neuro-developmental outcome when compared to the general population.

We propose that the children previously reported to have poor neurodevelopmental outcomes included a proportion of misdiagnosed children. Specifically, we postulate poor outcome is not a result of isolated ventriculomegaly, but rather due to additional conditions

not diagnosed by ultrasound. In these cases MR imaging may have found another brain abnormality.

8. Study supervision

The MERIDIAN study group proposes to continue with the same format of TMG, TSC and DMEC members as already exists, with the addition of a new member with neonatal/paediatric clinical experience.

9. Data handling and record keeping

Participant confidentiality will be respected at all times. As part of the screening process there may be a requirement for patient identifiable data to be passed by the University of Sheffield to the HSCIC for linkage and notification of any deaths. If the option to use HSCIC for death notification is implemented it will be ensured that regulatory approvals are in place and information governance policies adhered to, to monitor this process.

The site research staff may need to collect updated participant names and contact details so that participants can be contacted to arrange an appointment for project 2. These will be immediately entered with the existing MERIDIAN ID number on to a restricted section of the database, which may be accessed by the site research staff who entered the data, delegated staff at collaborating sites, and the study managers for follow up and verification of data. Access will be controlled by usernames and encrypted passwords. Participant contact details may need to be given to delegated Bayley's assessors, permission from the participant to pass on this information will be gained during the consent process.

All other data will be anonymised and will only be identifiable by MERIDIAN ID number. Data will be entered on to a centralised database held within the CTRU in Sheffield by a delegated research study member at the referring fetal medicine centre or at the University of Sheffield. This section will also be controlled by usernames and encrypted passwords.

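### Project 3 of the follow-up study: the analysis has no reference rate or bound for the no-increased-risk hypothesis, and may compare outcomes and prognoses from different sets of fetuses

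*Protocol*

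**What the plan says.** All references are to the 2-3 year follow-up protocol unless stated.

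- **Whose outcomes.** Section 2 (Project 3, objective 1a) plans "Identification of all isolated, mild ventriculomegaly cases diagnosed on in utero MR in the MERIDIAN cohort and define their developmental outcome at 2-3 years". Section 6 (Project 3) repeats this: "We will identify all cases of isolated mild ventriculomegaly diagnosed on iuMR".
- **Compared with what, in the objectives.** Objective 1b says only "Comparison of developmental outcome to the prognoses made based on USS". It names no separate set of cases.
- **Compared with what, in the analysis.** Section 7 (Analysis of Project 3) will "calculate the prevalence of severe and non-severe impairments from our data, together with exact binomial confidence intervals", and then "compare this to the prognoses obtained from cases where USS identified isolated mild VM". Its next sentence asks whether changes of prognosis after MR were due to further diagnoses.
- **Precision.** Section 7 (Sample size Project 3) assumes about 140 cases and a prevalence of poor outcome under 10%, and says "we will be able to estimate the prevalence to within a standard error of 2.5" per cent.
- **Hypothesis.** The hypothesis that closes section 7 is that MR-confirmed isolated mild VM does not raise the risk of a poor "neuro-developmental outcome when compared to the general population". The text below it proposes that earlier reports of poor outcome included misdiagnosed children, whose outcome reflects conditions that ultrasound did not show.

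**The concern.** The hypothesis, the analysis and the sample-size rationale address different questions. The hypothesis concerns the general population, but the analysis uses no general-population figure. A claim of no increase also needs a bound, because a wide interval that includes the reference rate does not show that the rate is the same.

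The comparison that is planned has its own difficulty. As section 7 words it, outcomes come from MR-diagnosed cases and prognoses from ultrasound-identified cases. The hypothesis text itself says that the ultrasound-labelled group contains children with additional conditions. A difference between outcome and prognosis could then reflect case mix rather than the quality of the ultrasound prognosis.

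Finally, the postulate about additional conditions needs outcomes in the fetuses that ultrasound labelled isolated and in which MR found more. Project 3 does not tabulate them.

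At stake is what parents and clinicians are told about isolated mild VM: a statement of no increased risk, or that ultrasound prognoses are too pessimistic, would go beyond what this analysis can show.

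**Working it through.** **1. The plan's own figure.** SE = √(p(1−p)/n). With p = 0.10 and n = 140, √(0.09/140) = 2.54%, which agrees with the stated 2.5%. At p = 0.05 it is 1.84%. The arithmetic is sound.

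**2. Attrition.** The protocol does not say whether 140 is before or after loss. Sample size Project 2 goes from about 500 survivors to about 400 cases, which can be read as 80%. Then n = 0.80 × 140 = 112, and the SE at 10% is √(0.09/112) = 2.8%. At 5% it is √(0.0475/112) = 2.1%, still inside 2.5%.

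**3. What 140 cases can say about the hypothesis.** The protocol gives no reference rate p0 and no margin, so both are assumed here. Limits are exact (Clopper-Pearson) 95%. Detecting a doubling means that the lower limit exceeds p0 when the true rate is 2·p0. Showing not increased means that the upper limit falls below p0 + margin when the true rate equals p0.

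| Assumed p0 | Events needed for lower limit > p0 | Chance of detecting a doubling | Not increased, margin 2.5 points | Margin 5 points | Margin 7.5 points |
|---|---|---|---|---|---|
| 3% | 10 | 33% | 21% | 59% | 94% |
| 5% | 13 | 65% | 17% | 45% | 84% |
| 10% | 22 | 92% | 10% | 35% | 68% |

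The conclusion depends almost wholly on two numbers that the protocol does not state. The figure of 10% is a planning assumption there, not a limit. As a guide to its use as one, 6/140 has an upper limit of 9.1% and 7/140 one of 10.03%.

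A reference rate cannot simply be taken from one score below 70. Severe impairment in Analysis of Project 2 is a composite of motor, cognitive and language scores, cerebral palsy and, where there is no Bayley assessment, the parent questionnaire.

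**4. How far the two groups could differ.** The main protocol's Introduction reports an earlier study in which MR found other relevant brain findings in 17% of fetuses with isolated VM on ultrasound. Assume poor outcome in 5-10% of truly isolated cases and 30-50% of the rest. The rate in the ultrasound-labelled group is 0.83 × a + 0.17 × b:

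- a = 5%, b = 30%: 9.3%
- a = 5%, b = 50%: 12.7%
- a = 10%, b = 30%: 13.4%
- a = 10%, b = 50%: 16.8%

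So 5-10% in one group would stand beside 9-17% in the other. The rates a and b are illustrative.

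**5. Size of the untabulated group.** If all 140 were also labelled isolated on ultrasound and the 17% applied, the ultrasound-labelled group would be 140/0.83 ≈ 169, leaving about 29 with additional findings. With 9/29 poor outcomes (31%), the exact interval is 15% to 51%.

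**The case against.** Several stronger readings are tempting, and the documents do not support them.

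- *Project 3 cannot answer its question.* Too broad. The aim of describing outcome in MR-diagnosed cases is met by a prevalence with an exact interval, at about the stated precision.
- *There is no comparator.* The general population is named. What is absent is its rate or source, a bound, and any analysis that uses it. The source might be left to an analysis plan. That does not cure the mismatch, because the protocol itself fixes a hypothesis, an analysis and a sample-size rationale that do not meet.
- *The groups are certainly different.* Objective 1b can be read as the ultrasound prognoses of the same MR-diagnosed children, and the two groups overlap. The sections are inconsistent and need reconciling.
- *MR-diagnosed children must look better than their ultrasound prognosis.* Not certain. The commonest ultrasound prognosis is favourable, which the main protocol (section 3) defines as more than a 90% chance of normal outcome. Section 6 counts 85 and above as normal. If scores had mean 100 and SD 15 (an assumption), 15.9% of average children would fall below 85, so average children could look worse than that prognosis.
- *The MR-found-additional group is not followed up.* The study aims to include all surviving children, and Project 2 reviews cases in which the two prognoses differed. What is missing is an outcome table for this group. The sentence in Project 3 on changed prognoses concerns why prognosis changed, not what happened to the children.
- *An imprecise result will be reported as no association.* The protocol states no such rule and plans exact intervals. The risk is that nothing in the plan prevents it.
- *Precision will be much worse than stated.* No retention below the 80% reading appears in the document.

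**Conclusion.** The point holds in limited form and should be fixed. The claim of no increased risk and the additional-conditions postulate are not supported by the analysis as written. The prevalence estimate is. The objectives and the analysis also disagree on whose ultrasound prognoses are used, and under the wording in section 7 the comparison is open to case-mix differences of uncertain direction.

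The size depends on assumptions. Across reference rates of 3% to 10%, the chance of detecting a doubling with 140 cases runs from 33% to 92%. At 5%, the chance of showing not increased runs from 17% to 84% as the margin goes from 2.5 to 7.5 points. The group contrast in step 4 rests on the 17% from the earlier study and on assumed outcome rates. The attrition effect is minor: 2.8% in place of 2.5% at a prevalence of 10%.

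**What to change.** 1. Reconcile objective 1b in section 2 with Analysis of Project 3 in section 7, so that outcome and ultrasound prognosis are compared in the same children.
2. Take all fetuses labelled isolated mild VM on ultrasound and split them into MR-confirmed and MR-found-additional. Tabulate ultrasound prognosis, MR prognosis and outcome in each, with exact intervals and the risk difference. State that deaths and terminations are handled as in Project 2.
3. Then choose one of two courses. Either state a general-population rate for the same composite outcome, its source, and an upper bound for not increased; or restate the hypothesis as estimation of prevalence with its exact interval, and say that a non-significant result will not be taken as no increased risk. Adopting 10% as a decision limit is possible but has a cost: with 140 cases it needs 6 or fewer events, which happens only 45% of the time if the true rate is 5%.
4. Say whether 140 is before or after attrition, and restate the standard error for the number expected to be assessed.

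The cost is wording and one table, from data that Project 2 already sets out to collect. The downsides are a more modest conclusion and a small MR-found-additional group, with wide intervals there.
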